
Primary aim. To compare total MPA (min/wk.) across the 6-mo. active intervention in adults with AD and their caregiver randomized to RGV and EUC. We expect greater MPA in the RGV compared to EUC arm.

Secondary aims: To compare the following across 18 mos. between RGV and EUC. *Adults with AD:* MPA (min/wk.), sedentary time (min/wk.), percentage meeting 150 min/wk. goal, functional fitness, activities of daily living (basic/instrumental), quality of life, residential transitions, neuropsychiatric symptoms, cognitive function. *Caregivers:* Total MPA (min/wk.), sedentary time (min/wk.), functional fitness, quality of life, caregiver burden. We expect more favorable changes for all secondary outcomes for both adults with AD and caregivers in the RGV compared with the EUC arm.

Exploratory aim. To evaluate the influence of process variables/ characteristics on MPA in adults with AD and their caregiver across 18 mos.: age, sex, BMI, attendance (exercise/support sessions), use of recorded sessions, PA self-monitoring, peer interactions during group sessions, caregiver support, level of dementia.

B. Background and Significance

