
RGV arm

Schedule. Group exercise sessions will be scheduled on 3 non-consecutive days/wk.(M,W,F) during the active intervention (0 to 6 mos.) and 1 day/wk. during maintenance (mos. 7-12). Group sessions will not be scheduled during the no-contact period (13-18 mos.). During orientation sessions, dyads will be asked to provide times of the day, between 10 a.m. and 7 p.m., that would be most convenient to complete the group sessions. Based on this information we will offer dyads in each cohort the choice between 2 potential session times each day. Prompts reminding adults with AD/caregivers of upcoming sessions will be sent using iMessage on the iPad® (adult with AD)/iPod® (caregiver) and iCalendar. Session delivery. Real-time exercise sessions will be delivered to adults with AD/caregiver dyads in their home by a trained health coach experienced in working with adults with AD using Zoom® video conferencing software. This software allows multiple users to see and interact with each other and the health coach via the iPad®. The health coach will conduct exercise sessions from our remote-delivery exercise studio (see facilities) which we used for remote delivery of exercise in our AD pilot (61) and in trials with adolescents with intellectual and developmental disabilities (IDD) (62), and adults with Down Syndrome (63). Tutorials describing trouble shooting for common technical problems with the Zoom® software, e.g., internet connectivity etc., will be loaded on the iPad®. Dyads with technical issues during the intervention may also contact research staff by phone or email. An alternative caregiver (other family member, staff etc.) may participate in the event that the caregiver enrolled in the trial is unable to attend an exercise session. These procedures were used in our AD pilot trial where alternative caregivers attended 8% of sessions (61). MPA session content. [name], a physical therapist, will develop the exercise program for this trial. He developed the exercise content for our pilot trial in adults with AD and has been involved in other exercise trials for adults with AD (R01AG034614, R01AG033673) (64-66). Each session will include a warm-up (~5 min), moderate intensity aerobic activity (3-5 METs) (~30 min), resistance and balance/coordination exercise (~5 min.), and cool-down/stretching (~5 min.). The MPA portion will ramp from 10 min/session at wk. 1 to the goal of 30 min/session at wk. 8. Each session will include aerobic activity, e.g., walking/jogging standing in place or sitting in a chair, sit to stand, dance movements; resistance exercise, e.g., TheraBand®-arm curls, leg extensions, side leg raises, and seated rows; and balance exercise, e.g. heel to toe walks, balance walk, and standing on one foot with/without support of a chair). [name] will provide modifications for participants having difficulty with any specific exercises. Health coaches will encourage interactions between participants during group sessions and ensure interactions between participants do not focus on dementia (67), but rather on issues relative to supporting their peer's efforts to increase MPA. Additionally, the Zoom app used for the sessions allows for messaging between participants during and after the group exercise sessions. Caregivers will be allowed to message the research staff and other caregivers for help and support both during the sessions and outside of the group sessions. We will keep copies of the messages sent to research staff on the KUMC P-Drive. Outside session MPA. Group exercise sessions will provide the potential to accumulate 90 min/wk. (3 sessions x 30 min/session) during the active intervention (0-6 mos.) and 30 min/wk. (1 session) during maintenance (7-12 mos.). Thus, MPA in addition to that accumulated in group sessions will be required to meet the MPA goal of 150 min/wk. To provide a transition from a sedentary to a more physically active lifestyle we will recommend goal of 45 min of MPA/wk. at wk. 1 and increase the goal by 15 min/wk.to reach the 150 min/wk. goal at wk. 8. We successfully used this MPA progression in previous trials in adults with AD (57). At the completion of each group session health coaches will provide a "weekly challenge" for participants to try a new activity or create and perform a new exercise routine etc. in order to reach the 150 min./wk. goal. Additionally, the NIA pamphlet "Exercise and Physical Activity: Your Everyday Guide" will be loaded on the iPad to assist participants in meeting the 150 min./wk. goal. Video recordings. Video recordings of all group exercise sessions will be uploaded to Dropbox®. Participants/caregivers will be encouraged to access video recordings using their iPads®/iPods® to assist with meeting the 150 min./wk. goal. Frequency and duration of participant/caregiver video access will be tracked using Dropbox® analytics. No contact follow up (13-18 mos.). Group video and individual support sessions will be discontinued. Participants will be

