Schedule. MPA in adults with AD and their caregiver will be assessed at baseline (1 wk. prior to starting the intervention), 3, 6, 12, and 18 mos. Equipment. MPA/sedentary time will be assessed using an ActiGraph model wGT3x-BT tri-axial accelerometer (3.3 x 4.6 x 3.5 cm, wt. = 19 g., dynamic range \pm 8 g). The ActiGraph provides valid and reliable assessments of MPA/sedentary time in adults (70-73). Our group has used the ActiGraph in several trials in a variety of populations including adolescents (74) and adults with IDD (75), and in typically developing children (76, 77) and adults (78, 79). Protocol. There is a lack of consensus on the best protocols to collect, process, and score ActiGraph data (80-82). Thus, our decisions regarding ActiGraph location, monitoring period, data processing etc. were based on current practice, as described below. Participants will be asked to wear the ActiGraph on a belt over the non-dominant hip at the anterior axillary line during waking hours for 7 consecutive days, except for bathing and swimming. A 7-day monitoring period provides a reliable estimate of MPA (81, 83-85). The hip, rather than the wrist location, will be used due to the lack of comparable data and established protocols for assessment of MPA using wrist-worn ActiGraphs (86-88). ActiGraph distribution/reminders. Research staff will distribute and

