demonstrate proper placement of the ActiGraphs at home visits scheduled at 0, 6, 12 and 18 mos. ActiGraphs will be distributed by mail for the 3-mo. assessment. Daily reminders to comply with the ActiGraph protocol will be sent to participant's iPad® each morning during the 7-day monitoring period. We have employed similar distribution and reminder protocols in previous trials (74 , 75-77, 79). Our current supply of ActiGraphs, plus the additional units requested in this proposal, will allow physical activity assessments to be completed on all participants in the proposed timeframe. Data collection. ActiGraphs will be initialized and downloaded using ActiLife Software version 6.13.3 or higher (ActiGraph Corp, Pensacola, FL) and set to collect in the raw data mode from all 3 axes at 60 Hz. Although the wGT3x-BT collects raw data from 3 axes, the widely used cut-points for determining activity intensity in adults proposed for this trial use acceleration data from the ActiGraph vertical axis (89). However, raw data from all 3 axes will be downloaded and stored, and will be available should algorithms for processing this data become available during this trial. Data processing Accelerometer data will be processed using the protocol for adults used in the 2003-2004 and 2005-2006 cycles of NHANES (89, 90). Data will be aggregated over 60-sec epochs. The following intensity cut-points will be used: sedentary (< 1.0 MET; ≤ 100 counts/min), light (1.1-2.99 METs; 101-2019 counts/min.), moderate (3.0-5.99 METs; 2020-5988 counts/min) and vigorous ≥ 6 METs; ≥ 5999 counts/min) (89, 90). Non-wear time will be defined as at least 60 consecutive minutes of zero counts, with allowance for 1-2 min of counts between 0 and 100. Counts ≥ 20,000/min will be considered spurious (91). All accelerometer data processing will be completed using custom SAS-/R programs developed by Drs. [name] and [name], the project statisticians, in collaboration with our research group. Missing accelerometer data. Recent advances in both statistical methods and computing power have made it possible to impute missing data with large data sets, such as will be collected in the proposed trial, i.e., 7 wk.-long assessments across 18 mos. A detailed description of the methods and procedures for handling missing ActiGraph data (non-wear and device malfunction time) is included in the analysis plan. MPA data for both adults with AD and caregivers will be analyzed including and excluding video conference exercise sessions (RGV arm).

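### The 6- and 12-month ActiGraph weeks are not tied to the phase they represent; handover at or near the nominal date would put most or all of the 6-month primary week after RGV sessions drop from three to one a week

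*Combined protocol and SAP*

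**What the plan says.** The primary aim is "To compare total MPA (min/wk.) across the 6-mo. active intervention in adults with AD and their caregiver randomized to RGV and EUC".

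Under ASSESSMENTS, MPA, Schedule, MPA "will be assessed at baseline (1 wk. prior to starting the intervention), 3, 6, 12, and 18 mos". After baseline, the active phase is therefore sampled by one week at 3 months and one at 6 months.

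Under Protocol in the same section, the device is worn "during waking hours for 7 consecutive days, except for bathing and swimming". Under ActiGraph distribution/reminders, staff hand over the devices and "demonstrate proper placement of the ActiGraphs at home visits scheduled at 0, 6, 12 and 18 mos". The exception is month 3: "ActiGraphs will be distributed by mail for the 3-mo. assessment".

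Under RGV arm, Schedule, group sessions run on "3 non-consecutive days/wk.(M,W,F) during the active intervention (0 to 6 mos.) and 1 day/wk. during maintenance (mos. 7-12"), and then stop for the no-contact period. Under Outside session MPA, the group sessions offer the chance to "accumulate 90 min/wk. (3 sessions x 30 min/session) during the active intervention (0-6 mos.) and 30 min/wk. (1 session) during maintenance (7-12 mos".).

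The baseline week has an explicit position, before the intervention starts. The 6- and 12-month weeks have no position relative to the change of phase and no visit window. No rule says what to do with wear days that fall after the change.

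**The concern.** Wear cannot begin before the device is handed over. A visit held when month 6 ends therefore puts the wear week in month 7, when RGV dyads have one group session a week instead of three. EUC dyads have no group sessions in either phase, and the reduction in individual support sessions is the same in both arms. The loss of group sessions thus acts on one arm only and pulls the active-phase contrast towards zero.

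Interpretation is also at stake. The analysis section gives, as its example of a group-by-time interaction, an RGV advantage that grows in the later months. If the last point in the 0-6 month window is measured after a planned step-down, the model could show a fading effect that is only the session schedule. A week worn in the wrong phase cannot be recovered by later analysis.

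At 12 months the pattern repeats on a smaller scale (one session a week against none), for a secondary outcome.

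**Working it through.** **1. The plan's own power figure.** Inputs from Sample size, statistical methods, and power calculation: difference 10 min/d, SD 30 min/d, 21 measurements, correlation 0.22, 42 per arm. The 21 measurements fit three weeks of seven days (0, 3 and 6 months). Alpha is not stated; two-sided 0.05 is assumed.

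- SD of a participant's mean = 30 × √[(1 + 20 × 0.22)/21] = 30 × √(5.4/21) = 15.2 min/d.
- Standard error of the difference = 15.2 × √(2/42) = 3.32 min/d.
- Power = Φ(10/3.32 − 1.96) = Φ(1.05) ≈ 85%.

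This agrees with the stated 80% or more. The power calculation is not in dispute here.

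**2. How easily the week spills over.** All seven days stay in the active phase only if handover is about a week or more before the phase ends. As an assumption, let visits be spread evenly around the phase change:

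- Within ±7 days: half the visits put every wear day in maintenance and the other half put in 50% on average. 0.5 × 1 + 0.5 × 0.5 = 75% of wear days.
- Within ±14 days: 0.5 × 1 + 0.25 × 0.5 + 0.25 × 0 ≈ 63%.

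Scheduling that is centred on the nominal date therefore does not average out.

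**3. Size if the whole 6-month week falls in maintenance.** Pilot inputs for adults with AD, from Potential for video conferencing: three sessions a week, 20.4 min MPA per session, about 77% attendance, net gain in weekly MPA of 24 min. The planned difference is 10 min/d × 7 = 70 min/wk. The 3- and 6-month weeks are weighted equally.

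| Basis for losing two of three sessions | Loss, min/wk | Loss, min/d | Share of 70 | Month-6 difference, min/d | Mean of months 3 and 6, min/d | Power |
|---|---|---|---|---|---|---|
| Net gain: 2/3 × 24 | 16 | 2.3 | 23% | 7.7 | 8.9 | 76% |
| In-session minutes: 2 × 20.4 × 0.77 | 31.4 | 4.5 | 45% | 5.5 | 7.8 | 65% |

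First row: mean = (10 + 7.71)/2 = 8.86, a reduction of 1.14 min/d or about 11%; power = Φ(8.86/3.32 − 1.96) = Φ(0.71) ≈ 76%. Second row: Φ(7.76/3.32 − 1.96) = Φ(0.38) ≈ 65%.

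The first row is the better guide. Three pilot sessions supplied 3 × 20.4 × 0.77 = 47 min/wk in session, but total weekly MPA rose by only 24. Session minutes partly displaced other activity, so removing two sessions need not cost all their minutes.

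**4. Caregivers.** The document gives two pilot net gains, 49 min/wk (Potential for video conferencing) and 23 min/wk (opening summary). Two thirds is about 33 or 15 min/wk. The in-session equivalent is 2 × 27.0 × 0.79 = 43.

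**5. Month 12, adults with AD.** One session lost: 24/3 = 8 min/wk on the net basis, 20.4 × 0.77 = 16 in session.

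**The case against.** The strongest reply is that the month labels are nominal. The visit labelled 0 takes place before the intervention starts, so a visit labelled 6 could fall in the last active week. A visit during month 6 is inside the active phase, and the stated aim shows that this is what the authors intend. A strictly literal reading would even put the 18-month wear week after the 18-month trial has ended. This stands as far as it goes. A reader might infer that the final primary week definitely falls in maintenance, and the documents do not establish that. They leave the timing open, and the one assessment that is clearly placed relative to a phase is placed by an explicit statement that the later ones lack.

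A reader might also take the loss to be 31 min/wk, or 60 min/wk from the protocol's potential of 90 against 30 (8.6 min/d, mean difference 5.7 min/d, power about 41%). The first treats all session minutes as additional, which the pilot's net gain contradicts. The second also assumes full attendance and a full 30 minutes of MPA per session. Neither is a forecast.

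Three mitigations are fair. The 150 min/wk goal continues after month 6 and recorded sessions remain available, so some activity may be replaced. The pilot minutes come from a Fitbit, whereas the trial outcome uses a hip ActiGraph. MPA will also be analysed with video sessions excluded, and that analysis is not directly changed by how many sessions the week contains. It answers a different question, however, and does not repair the main comparison.

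**Conclusion.** The point holds in conditional form. The plan does not tie the 6- and 12-month wear weeks to the phase they represent, and handover at or near the nominal date puts most or all of the 6-month week after the RGV step-down. The resulting bias would run in one direction, towards a smaller active-phase difference. It has not been shown that visits will be timed this way.

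If the whole 6-month week falls in maintenance and lost activity is not replaced, a reasonable illustration is 16 min/wk in adults with AD. That is 23% of the planned difference at month 6 and 11% averaged over months 3 and 6, with power going from about 85% to about 76%. The in-session figure of 31 min/wk, with power of about 65%, is an upper illustration. Both rest on a true active-phase difference of 10 min/d, an immediate drop, equal weight for the two weeks, 42 per arm, 21 measurements, correlation 0.22 and two-sided 0.05. Partial overlap or replacement activity would make the effect smaller. The month-12 issue is lesser. This should be fixed; confidence is moderate, because the actual visit timing is unknown.

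**What to change.** Under ASSESSMENTS, MPA (Schedule and ActiGraph distribution/reminders):

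- State that the 6-month wear week must be completed before sessions change to one a week, and the 12-month wear week before sessions stop.
- Schedule the handover visits early enough for this, for example 8 to 10 days before the phase ends, and give a visit window.
- Flag any wear day after the phase change. Add a sensitivity analysis that excludes those days from the 0-6 month comparison.

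No extra visits, devices or participants are needed. The cost is that the other 6- and 12-month home assessments also move about 10 days earlier. If visits are already scheduled this way, one sentence recording it is enough.

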Removal from the Study. If the study present greater then minimal risk to a participant they will be censored from the study and referred to the University of Kansas Alzheimer's Disease Center for recommendations for other resources for PA. All participants and caregivers will be informed that they may be censored from the study due to safety risk during the consent procedure. We believe the following scenarios would present a greater than minimal risk to participants. Lack of caregiver. A caregiver will be asked to participate in the intervention with the adult with AD. Many caregivers will be older adults and it is possible some may become deceased, become ill or hospitalized and unable to provide care to the AD individual. If this happens, the adult with AD will be asked to identify another individual to serve as the official study caregiver. If an alternative caregiver cannot be identified the individual with AD will be censored from the study from that time forward.

Transition to a residential facility. Some adults with AD may be placed in a residential care facility during the 18-mo. intervention. If this occurs the adult with AD will be censored from the study.

Change in severity of AD. If dementia progresses to the point that either the caregiver or research staff feel the intervention is no longer safe for the individual, they will be censored from the study. If an individual with AD is removed from the study for one of the aforementioned reasons (transition to residential facility or change in severity of AD), decides to no longer participate in the intervention, or dies during the intervention, the caregiver will be allowed to continue in the intervention, if they choose. If a caregiver stays enrolled in the intervention without the person with AD we will no longer collect outcomes regarding Caregiver Burden or Quality of the dyadic relationship.

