The study statisticians [name] and [name] will review of the rate of subject accrual and adherence to inclusion/exclusion criteria will occur quarterly to assure that participants meet eligibility criteria and ethnic diversity goals outlined in the grant proposal.

Measurement and Reporting of Participant Compliance to the Treatment Protocol.

Compliance to the intervention will be reported monthly by the study statisticians. To monitor compliance, they will report the group attendance at group exercise sessions (RGV) and/or individual health education sessions (EUC). Compliance to the intervention protocol will be reviewed monthly by the MPIs. We are using an intent-to-treat design; thus, participants will not be dismissed for non-compliance, but will be counseled on strategies to improve compliance during scheduled FTF or RD sessions.

Safety Officer. The safety officer for this trial will be [name]. [name] is a Neurologist at the University of Kansas Alzheimer's Disease Center and is not affiliated with the study in any other fashion and is not in the MPI's chain of command. zhe will review the reports sent by the study coordinator semi-annually and adverse events as they occur and will use the checklists attached to this document to determine whether there is any action, such as an ad hoc review or stopping rule violation that should be communicated to the study investigators, The University of Kansas Human Subjects Committee, or NIH. In addition, the safety officer may comment on whether the study investigator needs to report any specific out of range laboratory data to the participant, and/or their physician.

II. Subject Participation

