Missing data. Missing data is anticipated due to either attrition, e.g., participant dropout, or nonresponse, e.g., ActiGraph non-wear or malfunction. Our intent-to-treat approach will employ full information maximum likelihood (FIML) estimation in the modeling, which does not discard participants who dropped out but utilizes all available data from their partial measurements, thereby producing unbiased parameter estimates and smallest possible standard errors. Missing observations due to nonresponse will be handled by Monte Carlo Markov Chain (MCMC) multiple imputation (MI) (114). A sufficient number of imputed datasets will be created to ensure accurate recovery of missing data and analysis results from each imputed dataset will be combined to make valid statistical inferences. Our imputation process will incorporate a number of auxiliary variables, thereby satisfying the missing at random (MAR) assumption (115). The state-of-the-science on missing data indicates that FIML and MI are extremely robust and leads to unbiased generalizability (116).

V. Bibliography / References / Literature Cited

1. Alzheimer's Association. Alzheimer's Disease Facts and Figures: Alzheimer's & Dementia 2017. 2017.

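### Adults with AD who are removed for placement, progression or loss of a caregiver have no planned later assessment, yet the FIML analysis is called intent-to-treat and unbiased with no sensitivity analysis

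*Combined protocol and SAP*

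**What the plan says.** Section F, Removal from the Study, lists three situations that end an adult's participation.

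- Placement in a residential facility: "If this occurs the adult with AD will be censored from the study".
- Loss of the caregiver, but only where nobody can take over: "If an alternative caregiver cannot be identified the individual with AD will be censored from the study from that time forward".
- Progression of dementia to the point where the caregiver or research staff "feel the intervention is no longer safe for the individual, they will be censored from the study".

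After removal for placement or progression, "the caregiver will be allowed to continue in the intervention, if they choose". Nothing is said about further assessment of the adult with AD.

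Section G, on participant compliance, states: "We are using an intent-to-treat design; thus, participants will not be dismissed for non-compliance". The Missing data paragraph of the statistical section also calls the analysis intent-to-treat. It splits missing data in two. Attrition is handled by FIML on whatever was observed, and the resulting estimates are described as unbiased. Nonresponse, such as ActiGraph non-wear or malfunction, is handled by multiple imputation with auxiliary variables, "thereby satisfying the missing at random (MAR) assumption". The Baseline equivalence paragraph adds adjustment for variables that differ significantly between dropouts and completers. No estimand is defined for removed participants, and no analysis examines departures from MAR.

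**The concern.** The wording removes people from the study, not only from the exercise programme. Placement, unsafe progression and loss of support are plausibly related to later moderate physical activity (MPA), function and cognition. If measurement stops at those events, FIML in effect continues each removed person along the course predicted by their own earlier data and by those who remain in the same arm. For a removed RGV participant, that is the course of someone still attending sessions.

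The estimate then describes a setting in which nobody is removed, while the label suggests an effect in everyone randomised. If benefit stops at removal, the two differ. The 18-month secondary outcomes are more exposed than the 0-6 month primary outcome: removals accumulate, and progression ends collection of the functional and cognitive measures it would most affect. Residential transition is both a removal trigger and a secondary outcome.

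**Working it through.** **Inputs from the plan.** Sample size section: difference 10 min/d, SD 30 min/d, 21 MPA measurements, correlation 0.22, attrition about 20%, at least 42 per arm remaining. Design section: 100 dyads randomised 1:1, so 50 per arm. Assessments section: MPA at 0, 3, 6, 12 and 18 months. Pilot baseline in adults with AD: 53.9 min/wk, or 53.9/7 = 7.7 min/d.

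**Assumptions.** Removal shares by arm, their timing and the benefit kept after removal are not documented, so ranges are shown. Alpha is not stated; 0.05 two-sided is used.

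**1. The plan's own power.** SD of a participant's mean of 21 measurements = 30 × √((1 + 20 × 0.22)/21) = 30 × √(5.4/21) = 15.21 min/d. Power for 10 min/d is 85.4% at 42 per arm and 83.6% at 40 (50 × 0.8). The stated figure of at least 80% is reproduced.

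**2. Six-month difference with equal removal.** Let q be the share removed by month 6 in each arm, and let removed RGV participants lose all benefit. The all-randomised difference is 10 × (1 − q). The MAR estimate stays near 10, so the overstatement is 1/(1 − q) − 1. If half the benefit persists, the difference is 10 × (1 − q/2).

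| q | All benefit lost (min/d) | Overstatement | Half persists (min/d) | Power for the all-lost difference, 50 per arm followed |
|---|---|---|---|---|
| 5% | 9.5 | 5% | 9.75 | 87.7% |
| 10% | 9.0 | 11% | 9.5 | 84.1% |
| 16% (42 of 50 left) | 8.4 | 19% | 9.2 | 78.8% |
| 20% | 8.0 | 25% | 9.0 | 74.8% |

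In weekly units the last row is 8.0 × 7 = 56 min/wk against 10 × 7 = 70.

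**3. Does a likelihood analysis behave this way?** Simulated visits at 0, 3 and 6 months, with half of the removals before month 3, were fitted by maximum likelihood with arm-by-visit means and an unstructured covariance. With all benefit lost at q = 5%, 10% and 20%, the 6-month estimate was 10.1, 10.0 and 9.9; the difference in everyone randomised was 9.6, 9.0 and 7.9. With half the benefit lost at 20%, it was 9.9 against 8.9. With benefit retained, it was 9.8 against 9.9, so no material bias.

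**4. Timing.** The primary model looks at the group effect across time, and people removed after month 3 still contribute that visit. Weighting months 3 and 6 equally, with all 20% being removals and no benefit kept:

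- Lost evenly over 18 months: 20% × 3/18 = 3.3% by month 3 and 20% × 6/18 = 6.7% by month 6. Mean 5%; 1/0.95 − 1 = about 5%.
- Lost evenly by month 6: 10% and 20%. Mean 15%; 1/0.85 − 1 = about 18%.

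**5. Direction with unequal removal.** Take EUC at 7.7 and RGV at 17.7 min/d, with MPA falling to 0 after removal in either arm:

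- RGV 20%, EUC 10%: 0.8 × 17.7 − 0.9 × 7.7 = 7.23. A MAR estimate of 10 is 2.77 too high.
- RGV 10%, EUC 20%: 0.9 × 17.7 − 0.8 × 7.7 = 9.77. It is 0.23 too high.
- RGV 5%, EUC 20%: 0.95 × 17.7 − 0.8 × 7.7 = 10.655. It is about 0.65 too low.

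**The case against.** The plan does more than drop people. FIML keeps every observation made before removal, dropout-related variables are adjusted for, and a lost caregiver can be replaced. The intent-to-treat sentence in section G is tied to non-compliance and is not contradicted by removal for safety. Much of the attrition may be ordinary dropout or fall after month 6, which would leave the primary outcome little affected. All of this stands, and it limits the size. It does not make the data MAR: adjusting for variables that differ between dropouts and completers cannot recover what happened after removal.

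Four stronger readings are tempting but not supported.

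- A reader might infer that the sentence about auxiliary variables and MAR is the plan's claim about removals. It concerns imputation for nonresponse; removals fall under the FIML statement. Both claims are too strong, but they are separate.
- A reader might infer that the plan expressly stops outcome collection. It says only that the person is censored from the study.
- A reader might infer that the RGV effect will be overstated. That depends on benefit being lost and on the balance of removals. The trial itself expects RGV to do better on residential transitions, which could mean more placement removals in EUC.
- A reader might infer that more coach contact in RGV will trigger more removals for progression. Group sessions do give unblinded coaches more opportunity to notice decline. But caregivers in both arms can also trigger removal, and support sessions and weekly Fitbit checks are common to both. No figure in the documents settles it.

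**Conclusion.** The point holds as a conditional one. The plan provides no assessment after outcome-related removal, calls the resulting analysis intent-to-treat and unbiased, and has no means of showing how far the result depends on MAR.

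With equal removal and complete loss of benefit, the 6-month difference is overstated by about 5% to 25% as removal rises from 5% to 20%. The 25% is the upper end of that scenario: it treats all planned attrition as removals before the 6-month visit with nothing retained. Averaged over months 3 and 6, the corresponding figures are about 5% or 18%, depending on when the 20% is lost. Unequal removal can make the error larger or reverse it, and there is none if benefit persists. A single figure or a fixed direction would go beyond the documents. That uncertainty is the reason to collect the data and add a sensitivity analysis.

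**What to change.** - State that leaving the intervention does not by itself end outcome collection. With consent, continue the ActiGraph by mail, the route already used at 3 months, and caregiver-reported measures where a caregiver remains (the QOL-AD already has a caregiver form), at the scheduled visits.
- Record the reason and date of every removal, and report them by arm.
- Add one delta-adjusted or reference-based sensitivity analysis for data still missing after removal, by removal reason. Keep deaths apart, since nothing remains to be measured.
- In the Missing data paragraph, describe both the FIML estimates and the multiple imputation as valid if MAR holds.

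The criteria for removing someone from the intervention are not at issue and do not change.

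The cost is protocol and consent wording, some mailings and questionnaires, and one further analysis. The burden on families is modest. Uptake will be incomplete, especially where no caregiver remains or after placement, so the sensitivity analysis is needed even if follow-up is extended.
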